### **2.1.3 Exploratory Efficacy Objective**

The exploratory efficacy objective for this study is to further assess the efficacy of ocrelizumab 600 mg IV given every 24 weeks by monitoring patient-reported outcomes (PROs) related to quality of life (QoL), treatment satisfaction and other endpoints or analyses as follows:

- Multiple Sclerosis Impact Scale (MSIS)-29 (MS-specific QoL questionnaire)
- Treatment satisfaction questionnaire for medication (TSQM II)
- Patient reported outcome: SymptoMScreen
- MRI and clinical outcomes at 6 months and 1 year
- Predictors of NEDA and association between NEDA and disability or other efficacy parameters
- Severity of relapses (hospitalization for MS relapse, use of corticosteroids, residual disability)
- Employment status (WPAl)
- Proportion of patients who have NEDA, as per protocol defined events during a 96-week period and starting from baseline

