### **6.4.4        Analysis Methods**

The analysis will be performed after the last CDP and CDI confirmation visit. The per-protocol population will be used for supportive efficacy analyses of the primary endpoint.

The evaluation of the clinical efficacy of ocrelizumab will be based upon the events in-between baseline visit and week 96. The MRI activity is evaluated from week 8 to week

96. The proportion of patients free from protocol-defined events up to Week 96 (i.e. patients with NEDA) will be calculated and the corresponding two-sided Clopper-Pearson 95% CI will be presented. Logistic regression models will be used to identify predictors of response to treatment (freedom from events). Variables that will be considered include: region, line of treatment (previous DMTs), gender, and baseline EDSS. In addition, specific efficacy endpoints, such as CDP, will be compared between patients with or without evidence of disease activity up to Week 96.

Details about the missing data handling, as well as sensitivity analyses, will be specified in the statistical analysis plan.

The proportion of patients free from a protocol-defined event up to Week 24, 48, and 96 will be calculated and the corresponding two-sided Clopper-Pearson 95% CI will be presented. Logistic regression models will be used to identify predictors of response to treatment (freedom from events). Variables that will be considered include: region, line of treatment (previous DMTs), gender, and baseline EDSS.

The annualized relapse rate by Week 96 will be analyzed using regression based on a negative binomial model, adjusting for factors that may include region, baseline EDSS (<4.0 vs  $\geq 4.0$ ), line of treatment (previous DMTs), with the log-transformed drug exposure time in years as an “offset” variable. The adjusted annualized relapse rate will be presented.

EDSS and its change from baseline, as well as other continuous variables such as the change in total T2 lesion volume and the key PROs, will be summarized descriptively at each assessment visit. The time course of these variables will be described using techniques such as linear mixed models for repeated measures (MMRM) adjusting for covariates such as the respective baseline score, geographical region, and baseline EDSS.

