2.3 DETERMINATION OF SAMPLE SIZE

With a sample size of 750 patients, an observed NEDA rate of 30% will be estimated with a precision (half-width of the 95% CI (Confidence Interval) around the estimate) of 3.3% based on the Clopper-Pearson method, i.e. the 95% CI will be (26.7%, 33.4%). Even if the NEDA rate is different from the assumed rate of 30%, with the proposed sample size the precision of the estimate will remain better than 3.6% (value for a NEDA rate of 50%).

The annualized relapse rate is another relevant outcome measure assessed in this study. Based on results from the pivotal Phase III studies NCT01247324 (OPERA I) and NCT01412333 (OPERA II), in this study the adjusted annualized relapse rate (ARR) assessed over two years is expected to be estimated with a precision of approximately 0.03.

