4. STATISTICAL METHODS

For continuous variables, descriptive statistics (e.g., number of patients [n], mean, standard deviation [SD], median, 25th and 75th percentiles, minimum, maximum) will be calculated and summarized.

For categorical variables, the number and percentage in each category will be displayed.

Statistical methods for analysis of efficacy variables are detailed in the Efficacy Analyses section below.

Unless otherwise specified, statistical tests will be two-sided and the statistical significance level will be 5%. Corresponding 95% CIs will be presented as appropriate. Although multiple statistical tests may be conducted, no adjustments to the Type 1 error rate will be made.

The analyses outlined in this SAP supersede those specified in the protocol.

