4.4 EFFICACY ANALYSIS

4.4.1 Primary Efficacy Endpoint

Protocol-defined event definition

The definition of a protocol-defined event of disease activity is the occurrence of at least one of the following individual events while on treatment with ocrelizumab:

- A protocol-defined relapse defined as an occurrence of new or worsening neurological symptoms attributable to MS. Symptoms must persist for > 24 hours and should not be attributable to confounding clinical factors (e.g., fever, infection, injury, adverse reactions to medications), and immediately be preceded by neurological stability for at least 30 days.
- 24-weeks CDP based on increase in EDSS while on treatment with ocrelizumab
- A new T1 Gd-enhanced lesion on MRI after week 8
- A new and/or enlarging T2 hyperintense lesion on MRI after week 8

The MRI activity will be calculated on the events starting from week 8 (baseline reset).

Patient without any of this protocol-defined event of disease activity will be considered as NEDA = Yes (no evidence of disease activity).

The primary endpoint, NEDA, as well as the related disease activities components and combinations listed below, will be evaluated on the mITT population based on the following analysis principles:

- Patients, who discontinued treatment prior week 96 due to death or lack of efficacy, will be considered as having evidence of disease activity at the time of treatment discontinuation (e.g NEDA="NO", Relapse="Yes" and CDP="Yes").
- Patients who discontinued treatment for reasons other than death or lack of efficacy with no evidence of disease activity at the time of early treatment discontinuation will be excluded from the analysis as their disease activity status cannot be ascertained.

This is further summarized in the table below:

Endpoint	Patients who discontinued treatment without related disease activities prior week 96 due to:	
	death or lack of efficacy	Other reason than death or lack of efficacy with no evidence of disease activity
NEDA	included with evidence of disease activity (NEDA=NO)	excluded
Relapse	included with evidence of disease activity (Relapse=Yes)	excluded

24-weeks CDP	included with evidence of disease activity (CDP="Yes")	
 • If discontinuation before confirmation, excluded • If discontinuation after confirmation, included when CDP="Yes"
T1 Gd-enhanced lesions after week 8	included with evidence of disease activity	excluded

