This analysis can be considered as a sensitivity analysis of primary endpoint looking at clinical and MRI events in- between baseline visit and week 96. The MRI activity (T1 Gd-enhanced lesion and new/or enlarging T2 hyperintense lesion) will be evaluated from baseline to week 96.

Number and percentage of patients who have NEDA (yes, no) according to the presence of T1 Gd-enhanced lesion at Week 8 will be provided.

This endpoint will be analyzed similarly to the primary endpoint as described in section [4.4.1](#).

4.4.3.8 Predictors of NEDA and association between NEDA and disability or other efficacy parameters

Logistic regression models will be used to identify predictors of response to treatment (freedom from events). Variables that will be considered include:

- Duration since MS Symptom Onset (≤ 3 years, >3 and ≤ 5 years, >5 years and ≤ 10 years, >10 years),
- T2 volume at week 8 (since not available at screening),
- presence of T1 Gd-enhanced lesions at screening,
- presence of relapses prior screening as per CRF (Yes/No)
- number of previous DMTs (1, >1)
- baseline EDSS
- gender.

4.4.3.9 Epoch analysis of NEDA in Year 1 (Weeks 0 to Week 48) and Year 2 (Week 48-96)

This analysis will be performed on the mITT population. Note, this is an additional endpoint as compared with the protocol.

The analysis of NEDA in Year 1 will follow the same rule as in Section 4.4.2.1. For the definition of EDA events in Year 2, a new baseline at week 48 for CDP and MRI activity

will be considered. A cross tabulation table of patients with NEDA = Yes/No in Year 1 and Y2 will be also presented.

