4.4.5 Subgroup Analyses

The primary and the secondary efficacy endpoints will be summarized by the following subgroups, provided that they include at least 50 patients:

- Last DMT prior to study enrolment
 - Interferons (Interferon β 1a, Interferon β 1b, Peg Interferon β 1a)
 - Glatiramer acetate
 - Teriflunomide
 - Fingolimod
 - Dimethyl fumarate
 - Natalizumab
- Age (\leq 40 years, $>$ 40 years)
- Disease severity at inclusion and in disease history:
 - EDSS at baseline ($<$ 2.5, \geq 2.5)
 - Number of relapses over the year prior to inclusion (\leq 1, $>$ 1)
 - MRI at Week 8: presence of T1 Gd+ (Yes/No)
 - time between the qualifying disease activity event (last relapse prior to study) while on last DMT and 1st dose of ocrelizumab ($<$ 6 months, \geq 6 months)

In addition, changes in EDSS and ARR at week 96 will be summarized separately for patients with and without NEDA upto week 96. ARR will be only be repeated on the patients without NEDA up to week 96.

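### SAP 4.4.5 splits Week 96 EDSS change by NEDA status over the same 96 weeks, so part of any difference is built in and cannot by itself show that NEDA relates to disability

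*SAP*

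**What the plan says.** - **NEDA.** SAP 4.4.1: "Patient without any of this protocol-defined event of disease activity will be considered as NEDA = Yes". The events are a protocol-defined relapse, 24-week CDP, a T1 Gd-enhanced lesion after Week 8, and a new or enlarging T2 lesion after Week 8, counted up to Week 96.
- **Link to EDSS.** The same section defines CDP, for baseline EDSS up to 5.5, as a rise of at least 1 point held for 24 weeks (minimum 154 days). A rise first seen at Week 96 may be confirmed later. A protocol-defined relapse needs a rise of at least 0.5 on EDSS, or specified functional-system rises.
- **Split by NEDA status.** SAP 4.4.5: "changes in EDSS and ARR at week 96 will be summarized separately for patients with and without NEDA upto week 96". The next sentence confines ARR to patients without NEDA.
- **CDP.** Protocol 6.4.4: "specific efficacy endpoints, such as CDP, will be compared between patients with or without evidence of disease activity up to Week 96". The protocol synopsis and its copy in SAP Appendix 1 repeat this. SAP section 4 says that the SAP's analyses replace the protocol's, and the SAP body contains no comparison of CDP by NEDA status.
- **Aim.** Protocol 2.1.3 lists "Predictors of NEDA and association between NEDA and disability or other efficacy parameters", and SAP 2.2.3 keeps it. SAP 4.4.3.8 carries that title but specifies only a logistic model for predictors of NEDA.
- **Year 1 and Year 2.** SAP 4.4.3.9 re-baselines CDP and MRI activity at Week 48. It then adds: "A cross tabulation table of patients with NEDA = Yes/No in Year 1 and Y2 will be also presented".

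**The concern.** The grouping variable is partly made from the outcome, over the same window. A patient whose EDSS rises by a point and stays up is placed in the non-NEDA group because of that rise, and the mean EDSS change of the two groups is then set side by side. A Week 96 rise can even serve as the initial progression that decides the group, once it is confirmed later.

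The stake is the exploratory aim of relating NEDA to disability. Because SAP 4.4.3.8 models only predictors of NEDA, the EDSS split in 4.4.5 is the one analysis in the SAP body that sets 96-week NEDA status against disability. A reader who sees worse EDSS change in non-NEDA patients could take it as evidence that NEDA tracks disability. Some difference would appear even if MRI activity and relapses had no bearing on progression.

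**Working it through.** **Inputs from the documents.** SAP 2.3: "With a sample size of 750 patients, an observed NEDA rate of 30% will be estimated with a precision". This gives N = 750 and NEDA = 30%, so 225 patients with NEDA and 525 without. As a check, the exact Clopper-Pearson interval for 225/750 is 26.74% to 33.42% (half-width 3.34%), which agrees with the stated 26.7% to 33.4%. The plan gives no figure for the split by NEDA status.

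**Assumptions.** The documents give no overall CDP rate, ARR or EDSS variability for this trial, so ranges are used. Equal follow-up is assumed.

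**Step 1: CDP.** By definition P(CDP | NEDA) = 0. All CDP therefore falls in the other group: P(CDP | no NEDA) = P(CDP) / (1 − P(NEDA)).

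| Assumed overall CDP | With NEDA | Without NEDA (30% NEDA) |
|---|---|---|
| 5% | 0% | 0.05/0.70 = 7.1% |
| 8% | 0% | 0.08/0.70 = 11.4% |
| 10% | 0% | 0.10/0.70 = 14.3% |

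A simulation of 2,000,000 patients, with relapse, CDP and MRI activity generated independently and NEDA set to 30%, gave 7.1% and 14.2% for the first and last rows. With 225 versus 525 patients, Fisher's exact p is 0.008 at 2% overall CDP, 1.4 × 10⁻⁶ at 5% and 5 × 10⁻¹³ at 10%, although no association was generated. The imputation in SAP 4.4.1 adds to the overlap: discontinuation for lack of efficacy or death counts both as non-NEDA and as CDP.

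**Step 2: ARR.** Protocol-defined ARR with NEDA is 0. Without NEDA it is overall ARR / (1 − P(NEDA)), that is 1/0.70 = 1.43 times overall. Assumed overall rates of 0.10 and 0.20 become 0.143 and 0.286. If NEDA were 50% or 75%, the multiplier would be 2.0 or 4.0.

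**Step 3: EDSS change.** Here the overlap is partial. Assume measurement noise with SD 0.6 and a 1.25-point shift in patients with CDP. The expected change without NEDA is then 1.25 × P(CDP)/0.70, which is 0.09, 0.18 and 0.27 points for overall CDP of 5%, 10% and 15%. With NEDA it is about 0. The simulation gave the same values. It carries only the CDP route and leaves out EDSS rises that accompany relapses.

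**Step 4: designs without the overlap, same no-association model (ARR 0.15, CDP 10%).**
- Year 1 NEDA against Year 2 outcomes: Year 2 CDP 5.15% with NEDA versus 5.13% without; Year 2 ARR 0.149 versus 0.151.
- Grouping by MRI activity alone (inactive versus active): CDP 9.9% versus 10.0%; EDSS change 0.126 versus 0.125; ARR 0.151 versus 0.151.

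The artefact disappears in both. The landmark simulation treats Year 1 CDP as settled at Week 48, so it does not test late confirmation. Under SAP 4.4.1 a rise first seen at Week 48 needs at least 154 further days and is confirmed at about Week 72, inside the proposed outcome window. CDP confirmed by Week 48 (day 336) must have begun by about day 336 − 154 = 182, or Week 26.

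**The case against.** The case on the other side has five parts.

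- **Only EDSS change is left as a two-group table in the SAP body.** A reader might infer that EDSS change, ARR and CDP are all compared by NEDA status. The SAP does not support that. The sentence after the ARR statement confines ARR to non-NEDA patients, and the CDP comparison survives only in the protocol and the copied synopsis, which the SAP overrides. This stands. The two ARR sentences still conflict, and nothing says outright that the CDP comparison is dropped.
- **EDSS change is not fixed by definition.** It is tempting to say that NEDA rules out EDSS worsening. It does not: half-point rises, and larger rises that are never confirmed, can occur with NEDA. This stands, so the contrast is biased rather than empty.
- **The table is descriptive.** SAP 4.4.5 specifies a summary with no test by NEDA status, Protocol section 6 calls the study exploratory, and nothing in 4.4.5 says the table answers the association aim. This lowers the stakes. However, no other analysis in the SAP body addresses that aim for 96-week NEDA status.
- **Later outcomes belong to the extension.** Protocol 3.2 and 4.6.4 assign the relationship between the primary endpoint and long-term outcome to the extension study. That is true, but this trial lists its own association aim.
- **SAP 4.4.3.9 already looks forward.** Its cross-tabulation separates Year 1 from Year 2 and should not be read as sharing the 4.4.5 defect. It relates NEDA to NEDA, however, and not to disability.

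**Conclusion.** The point holds in a limited form. The same-window EDSS contrast is biased by construction but not fully determined. It cannot by itself support an association between NEDA and disability. The protocol's CDP comparison is fully circular: 0% against 7.1% to 14.3% for overall CDP of 5% to 10% at 30% NEDA. ARR reported in non-NEDA patients alone is about 1.43 times the overall rate through selection.

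The zero in the NEDA group needs no assumption. The other sizes rest on the plan's 30% NEDA rate and on assumed CDP and relapse rates. The 0.09 to 0.27 EDSS points also rest on an assumed shift and noise, and are illustrative.

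A reader might go further and infer that the primary result is compromised. The documents do not support this: the NEDA proportion and its interval do not use this split. It is a low-cost improvement to an exploratory analysis.

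**What to change.** 1. **Add a Week 48 landmark analysis** to SAP 4.4.5 or 4.4.3.8, in patients still under observation at Week 48. Group by the Year 1 status already derived in 4.4.3.9. Summarise EDSS change from Week 48 to Week 96, Year 2 relapse rate, and CDP with onset after Week 48 measured from the Week 48 baseline. To keep Year 1 CDP from being confirmed inside the outcome window, either group by Year 1 MRI and relapse activity, or count in Year 1 only CDP confirmed by Week 48.
2. **Clarify the existing text.** Label the same-window EDSS table as descriptive, with components shared between grouping and outcome. State that the protocol's same-window CDP comparison is dropped. Reconcile the two ARR sentences, and if ARR is kept in non-NEDA patients only, note that selection raises it.

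**Cost.** SAP wording and a small amount of programming, with no new data collection. The landmark has a shorter outcome window, fewer CDP events, and only patients observed to Week 48. A relapse shortly before Week 48 may also leave a raised Week 48 EDSS that later falls, which should be noted beside the EDSS result.

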4.5 PHARMACOKINETIC AND PHARMACODYNAMIC ANALYSES

No pharmacokinetic or pharmacodynamics analyses are planned in this study

4.6 SAFETY ANALYSES

The safety outcome measures comprise the following: the incidence and nature of all adverse events, including findings on vital sign measurements, physical and neurological

examinations, clinical laboratory tests, locally reviewed MRI for safety (non-MS CNS pathology), and concomitant medications.

The safety analysis will be performed on the ITT population.

4.6.1 Exposure of Study Medication

Definitions

Dose: Ocrelizumab dose is given as one infusion or two infusions administered 2 weeks apart. Patients will be considered to have received a Dose of treatment if at least part of one infusion of that Dose (either Day 1 or Day 15 for dual infusions) was given. If a Dose is completely missed instead of delayed, the next dose number will be based on the number of previous doses received.

Treatment duration (in weeks) for a patient will be calculated as follows:

$$[(\text{Date of last contact}^* - \text{Date of first dose}) + 1] / 7$$

Treatment duration (in years) for a patient will be calculated as follows:

$$[(\text{Date of last contact}^* - \text{Date of first dose}) + 1] / 365.25$$

*Earliest 1) date of last contact from the study completion page or study early termination page

2) date of death

3) CCOD

Exposure Analysis

Exposure of ocrelizumab will be summarized using descriptive statistics with the following data:

- treatment duration (weeks),
- number of doses received (day 1 and day 15 infusions are considered as one dose)
- total cumulative dose (mg).

4.6.2 Adverse Events

For each recorded adverse event (AE), the term entered by the investigator describing the event (the “reported term”) will be assigned a standardized term (the “Preferred Term” [PT]) and assigned to a superclass term (the “System Organ Class” [SOC]) on the basis of the MedDRA World Health Organization (WHO) dictionary of terms.

Treatment emergent adverse events (TEAEs) will be summarized by SOC and PT. At each level of summarization (at least one event, SOC and PT), patients reporting more than one AE will be counted only once. For TEAEs by grade (intensity), the highest grade

will be reported. The table results will be sorted by descending frequency of SOC and PT within each SOC.

Summary of TEAEs will be repeated for the following subgroups, provided that they include at least 50 patients:

- Last DMT prior to study enrolment
 - Interferons (Interferon β 1a, Interferon β 1b, Peg Interferon β 1a)
 - Glatiramer acetate
 - Teriflunomide
 - Fingolimod
 - Dimethyl fumarate
 - Natalizumab

Definitions

Treatment-emergent adverse events (TEAE): AEs with an observed or imputed date of onset on or after the start date of trial treatment. If the onset date of the AE is prior to the day of first dose, the AE will be considered treatment-emergent only if the most extreme intensity is greater than the initial intensity (i.e., the intensity for a given AE increases and its end date is on or after the date of the first dose). An AE with a completely missing, non-imputed start date will be assumed to be treatment emergent unless the AE has a complete, non-imputed end date that is prior to the date of the first dose.

An adverse event will be considered as treatment-emergent in the period “baseline to week 24”, if the AE onset date occurred on or after the start date of trial treatment and before start date of trial treatment + 24 weeks. An adverse event will be considered as treatment-emergent in period “>= week X – week Y”, if the AE onset date occurred on or after the start date of trial treatment + week X and before start date of trial treatment + Y weeks. If the emergence of an AE cannot be clearly assigned to a period, the AE will be considered emergent across all appropriate periods.

Imputation of incomplete date: in order to evaluate if an AE is treatment-emergent, incomplete dates will be imputed as follows:

- If the start date is incomplete:
 - If the day is missing, impute to 01
 - If the day and months are missing, impute to 01JAN
 - If the date is completely missing, it is considered treatment-emergent
- If the end date is incomplete:
 - If the day is missing, impute to the last day of the month
 - If the day and month are missing, impute to 31DEC
 - If the date is completely missing, it is considered treatment emergent

Serious Adverse events (SAEs): all SAEs including serious MS relapses and serious Infusion Related Reactions (IRRs).

Dose assigned to an AE: only applicable if the AE onset date is on or after the date of the first infusion of that dose but before the first infusion of the next treatment dose. AEs that are reported during the safety follow-up period will be assigned to the last dose received. AEs that start prior to the first dose and worsen during treatment (i.e., treatment-emergent) will be assigned to the first treatment dose.

Output Conventions

All analyses of AE data will be performed using the PTs unless otherwise specified.

For all summary tables, the AEs will be sorted by SOC (in decreasing order of overall incidence) and then by PT (in decreasing order of overall incidence). All summaries and listings of AEs will be based on the ITT population. Summaries of AEs will be generated to summarize the incidence of treatment-emergent AEs only (TEAE and AE are used exchangeable).

A listing of all AEs will be provided, including all relevant information (including -but not limited to- start date, end date and the corresponding study days, related to treatment, seriousness, Grade, treatment-emergence).

Incidence Analysis on number of the events and number of patients with at least one event:

Overview of TEAE, including

- AE
- Serious AE
- Death
- AE with fatal outcome
- Infusion related reaction (IRR)
- Serious infusion related reaction (IRR)
- Infections (using the MedDRA SOC of “Infections and Infestations.”)
- Serious infection (using the MedDRA SOC of “Infections and Infestations.”)
- AE leading to study drug discontinuation (“Drug Withdrawn” for the “Action taken with ocrelizumab due to SAE/AE” field in the “Adverse Event/IRR/MS Relapse” eCRF form)
- Serious AE leading to study drug discontinuation (“Drug Withdrawn” for the “Action taken with ocrelizumab due to SAE/AE” field in the “Adverse Event/IRR/MS Relapse” eCRF form)
- AE leading to dose modification/interruption
- Serious AE leading to dose modification/interruption

- AE related to study medication,
- AE of Grade ≥ 3

An epoch summary (baseline to week 24, week 24 to week 48, and week 48 to week 96) of TEAEs will be repeated including the number of events and number and proportion of patients with adverse events emerging and serious AE in each of the period (baseline to week 24, \geq week 24 – week 48, \geq week 48 – week 96) will be provided.

Summary tables presenting the number of patients who experienced a TEAE will be summarized by SOC and PT for the following:

- **All TEAEs**
An epoch summary (baseline to week 24, week 24 to week 48, and week 48 to week 96) of TEAEs. The number and proportion of patients with adverse events emerging in each of the period (baseline to week 24, \geq week 24 – week 48, \geq week 48 – week 96) will be provided.
- If an AE cannot be allocated to
- **Most Common TEAEs** reported by 5% or more of patients
- **TEAEs related to study drug** (“Yes” for the “Even suspected to be caused by ocrelizumab?” field on the “Adverse Event/IRR/MS Relapse” eCRF form)
- **TEAEs by Intensity Grade** (“1”, “2”, “3”, “4”, “5” for the “AE most extreme NCI CTCAE grade” field in the “Adverse Event/IRR/MS Relapse” eCRF form). Multiple occurrences of the same event within a patient will be counted once at the greatest intensity/highest grade for this PT. For AEs leading to death, the most extreme intensity will be overwritten by Grade 5 (death). Any AEs and the SOC overall rows of the summary table will count patients according to AEs by intensity (grade).
- **TEAEs by intensity Grade ≥ 3** (“3”, “4”, “5” for the “AE most extreme NCI CTCAE grade” field in the “Adverse Event/IRR/MS Relapse” eCRF form)
- **Serious TEAEs** (“Serious” for the “Is this event non-serious or serious?” field in the “Adverse Event/IRR/MS Relapse” eCRF form),
- **Serious TEAE related to study drug**
- **Serious TEAE by intensity Grade ≥ 3**
- **TEAEs that led to study drug discontinuation** (“Drug Withdrawn” for the “Action taken with ocrelizumab due to SAE/AE” field in the “Adverse Event/IRR/MS Relapse” eCRF form)
- **TEAEs that led to modification or interruption of study drug** (“Dose reduced” or “Dose temporarily interrupted” for the “Action taken with ocrelizumab due to SAE/AE” field in the “Adverse Event/IRR/MS Relapse” eCRF form)

- **Non-serious TEAEs reported by 5% or more of patients** (Note: table required for EudraCT and CT.gov disclosure registries)

Adverse events rates per 100 patient-years of exposure are defined as:
(total number of adverse events/total duration in the study) × 100.

Event rate per 100 PY will be presented on the following events:

- AE with fatal outcome
- infusion related reaction (IRR)
- Serious infusion related reaction (IRR)
- infections (based on SOC)
- serious infection (based on SOC)
- AE leading to study drug discontinuation (“Drug Withdrawn” for the “Action taken with ocrelizumab due to SAE/AE” field in the “Adverse Event/IRR/MS Relapse” eCRF form)
- Serious AE leading to study drug discontinuation (“Drug Withdrawn” for the “Action taken with ocrelizumab due to SAE/AE” field in the “Adverse Event/IRR/MS Relapse” eCRF form)
- AE leading to dose modification/interruption
- Serious AE leading to dose modification/interruption
- AE related to study medication,
- AE of Grade ≥ 3 .

All serious adverse events and deaths will be also listed.

